## 5. Study Design

### 5.1. Overall Design

This is a multicenter, open-label Phase 1b/2a study of NT-I7 in combination with pembrolizumab. The study will include a dose escalation phase (Phase 1b) followed by a dose expansion phase (Phase 2a) and a Biomarker cohort.

The Phase 1b is designed to assess the safety and tolerability, including determination of the MTD and/or the RP2D, of NT-I7 in combination with pembrolizumab in subjects with advanced solid tumors. The Phase 1b will follow the standard 3+3 study design. Three dose levels of NT-I7 are planned [DL 1 (480 µg/kg IM Q6W), DL 2 (960 µg/kg IM Q6W), and DL 3 (1200 µg/kg IM Q6W)], and up to 18 subjects will be enrolled (up to 6 subjects per dose level). Doses may be de-escalated to one or two levels (e.g., 360 or 240 µg/kg IM Q6W) depending on the pre-defined Dose-Limiting Toxicity (DLT) criteria. Pembrolizumab dose is fixed at 200 mg IV Q3W for all dose levels. Upon completion of Phase 1b, the MTD was not reached. There was 1 DLT (Grade 3 ALT increased) observed at the highest dose level tested (1,200 µg/kg; n=6 patients). The RP2D was determined to be NT-I7 1,200 µg/kg (IM Q6W) and pembrolizumab 200 mg (IV Q3W).

For Phase 2a, selected arms I, II, III, IV, and V will follow the Simon's minimax two-stage design which include the following indications: CPI-treated R/R tumors (TNBC, NSCLC, SCLC), and CPI-naïve R/R tumors (MSS-CRC and PC). Each arm will enroll up to 17 evaluable subjects in Stage 1 and, if the Go/No Go criterion is met, an additional 8 evaluable subjects in Stage 2 for a total of 25 evaluable subjects per arm. Exact 95% binomial Clopper-Pearson confidence interval estimates of ORR from each arm is planned to support the primary hypothesis tests. Study enrollment will continue while the first 17 subjects are undergoing evaluation to confirm response. Enrolment of up to 30 subjects per arm is planned to account for non-evaluable subjects and dropouts. Approximately 210 subjects are planned in total for the Phase 2a. Subjects in the Phase 2a will be treated at the RP2D for the combination as determined in the Phase 1b.

Arms IVa, Va, and the Biomarker Cohort will not follow the Simon's minimax two-stage design.

The Biomarker Cohort will enroll up to 10 evaluable subjects with CPI-naïve R/R Ovarian Cancer (OC). The starting dose level of NT-I7 is planned at 960 µg/kg IM Q6W to further evaluate the tolerability of the starting regimen. Pembrolizumab dose is fixed at 200 mg IV Q3W. Subjects who tolerate at least 4 cycles of treatment without Grade  $\geq 3$  AEs and all Grade 2 AEs have resolved to Grade  $\leq 1$ , the dose may be escalated to NT-I7 1200 µg/kg IM Q6W at Cycle 5. This cohort will test intra-patient dose escalation and collect samples for biomarker analyses at 2 different dosages.

One treatment cycle is defined as 21 days (3 weeks) with NT-I7 administered intramuscularly (IM) once every 6 weeks (Q6W), and pembrolizumab administered intravenously (IV) once

every 3 weeks (Q3W). On days where both drugs are given, pembrolizumab will be given prior to NT-I7. Completion of 35 cycles of administration (approximately 2 years) with pembrolizumab and NT-I7.

## 5.2. Rationale for Dose Selection

Completed clinical study of NT-I7 monotherapy in patients with advanced solid tumors (Study GX-I7-CA-003) demonstrated an increase of ALC and multiple T-cell subsets in the peripheral blood in a dose-dependent manner until 720  $\mu\text{g}/\text{kg}$  where the increases appeared to plateau. However, comparative tumor infiltrating lymphocytes (TIL) data in cancer patients is not yet available, although it is possible that higher TIL responses may be observed at doses higher than 720  $\mu\text{g}/\text{kg}$ . Further, our preclinical data also suggested a dose-dependent increase in the peripheral ALC which appeared to plateau out at 2.5 mg/kg (i.e., no significant difference between 2.5 mg/kg and the higher dose of 10 mg/kg), but there were significantly more TILs, especially CD8+ T cells, at the 10 mg/kg dose. This animal dose of 10 mg/kg roughly translates to 810  $\mu\text{g}/\text{kg}$  human dose. In addition, since 10 mg/kg was the highest dose tested in the animal model, it is not known whether higher doses would result in more TILs. Thus, both 960  $\mu\text{g}/\text{kg}$  and 1200  $\mu\text{g}/\text{kg}$  dose levels are selected for testing.

The 480  $\mu\text{g}/\text{kg}$  dose is chosen as the starting dose for NT-I7 based on the following rationales: 1) the safety profile of the combination, pembrolizumab + NT-I7, is not known; 2) based on the data from Study GX-I7-CA-003, 480  $\mu\text{g}/\text{kg}$  dose did increase peripheral ALC and multiple subsets of T cells, thus can potentially provide benefit to the patients; 3) there are large differences between 480  $\mu\text{g}/\text{kg}$ , 960  $\mu\text{g}/\text{kg}$ , and 1200  $\mu\text{g}/\text{kg}$  doses that may allow detection of the differences in pharmacodynamic parameters (e.g. peripheral ALC and TILs) between the three dose levels.

Hence, based on the preclinical and clinical data, 480, 960, and 1200  $\mu\text{g}/\text{kg}$  are selected for testing in this study.

## 5.3. Dose Escalation (Phase 1b)

The starting dose of NT-I7 will be 480  $\mu\text{g}/\text{kg}$ .

The 3 + 3 design will be conducted as follows. Initially, 3 subjects will be enrolled to a dose level; the occurrence of a single drug related DLT in one of these 3 subjects will prompt enrollment of up to 3 additional subjects to that same dose level. When more than 1 DLT occurs in  $\leq 6$  subjects in a dose level, dose escalation will be stopped, and this dose level will be identified as the non-tolerated dose. Doses between the non-tolerated dose and the preceding lower dose, where  $\leq 1$  DLT occurred, may be explored to more precisely define the MTD.

The DLT is defined in Section 6.2. The DLT evaluation period is the first 21 days (3 weeks) of study treatment (Cycle 1, Day 1 to 21).

The dose escalation decisions will be communicated to all study sites by regularly scheduled teleconferences and follow up email correspondence documenting the decision and rationale.

The RP2D will be selected according to the following logic, taking into account the MTD determination from the Dose Escalation Phase (Phase 1b) and the Maximum Effective Dose (MED) level which is defined as the dose level at which maximum effects on peripheral blood T-cell levels and intratumor T-cell levels are observed. The intratumor T-cell levels will dominate if the peripheral blood and intratumor T-cell levels differ. The available data will be assessed by the Data Monitoring Committee (DMC), which will include the Protocol PI, Study Medical Monitor, Study statistician, and NeoImmuneTech, Inc.'s designee to select the RP2D.

- If the MTD is determined AND
  - MTD = MED, then the RP2D = MTD = MED
  - MTD > MED, then the RP2D = MED
- If the MTD is not reached, then the RP2D = MED

Once the RP2D has been selected, the study will proceed to the Dose Expansion Phase (Phase 2a) to further evaluate RP2D in a larger number of subjects and selected tumor types.

#### 5.4. Dose Expansion (Phase 2a)

Subjects enrolled into the study during the dose expansion phase (Phase 2a) will be treated at the RP2D, which was determined to be 1200 µg/kg IM Q6W. Certain indications may be selected to expand in the expansion phase based on the emerging data.

For Phase 2a, Arms I, II, III, IV, and V will follow the Simon's two-stage minimax design. Arms IVa, Va, and the Biomarker Cohort OC will not follow the Simon's two-stage minimax design.

- Arm I : CPI-treated R/R TNBC
- Arm II : CPI-treated R/R NSCLC
- Arm III : CPI-treated R/R SCLC
- Arm IV : CPI-naïve R/R MSS-CRC
- Arm IVa: CPI-naïve R/R MSS-CRC
- Arm V : CPI-naïve R/R PC
- Arm Va : CPI-naïve R/R PC
- Biomarker Cohort: Ovarian Cancer

In Stage 1, up to 17 evaluable subjects per arm will be enrolled and treated. If at least one subject achieves objective response (complete response [CR] or partial response [PR]) in an arm, that arm may be expanded by enrolling up to 8 evaluable additional subjects in Stage 2. Study enrollment will continue while the first 17 subjects are undergoing evaluation to confirm response. If no objective response is observed in an arm during Stage 1, further enrollment will be stopped in that arm.

**5.5. Subject Expansion (Arm IVa and Va)**

[figure not shown]
The Subject Expansion Cohort is designed to further assess the clinical benefits of NT-I7 in combination with pembrolizumab in subjects enrolled in the 2 selected cohorts based on emerging data. Subjects will receive Pembrolizumab at 200 mg IV Q3W and NT-I7 1200  $\mu$ g/kg IM Q6W.

**5.6. Biomarker Cohort**

[figure not shown]
The Biomarker Cohort is designed to assess the correlation between tumor infiltrating lymphocytes (TILs) and clinical benefits of NT-I7 in combination with pembrolizumab in subjects with CPI-naïve R/R Ovarian Cancer (OC). Up to 10 evaluable subjects will be enrolled in this cohort. The starting dose of NT-I7 will be 960  $\mu$ g/kg IM Q6W. Pembrolizumab dose is fixed at 200 mg IV Q3W.

Subjects who tolerate at least 4 cycles of treatment without Grade  $\geq$  3 AEs and all Grade 2 AEs have resolved to Grade  $\leq$  1 may be dose escalated to NT-I7 1200  $\mu$ g/kg IM Q6W.

## 5.7. Study Schema

## 5.8. Treatment Schema

Radiological tumor assessments will be conducted every 2 cycles (6 weeks  $\pm$ 1 week) during the first 6 months, and every 3 cycles (9 weeks  $\pm$ 1 week) thereafter. Confirmatory scans must be performed at >4 weeks after initial assessment of response to confirm a best response of CR or PR, whenever disease progression is suspected (e.g., symptomatic deterioration), and at End of Treatment visit. If disease progression is identified by RECIST 1.1, a second scan will be scheduled 4-8 weeks later to confirm disease progression by iRECIST. (See Section 13 and Appendix A for details).

### Tumor Biopsy

Pre-treatment biopsy/tissue collection (fresh) must be obtained within 28 days prior to Cycle 1, Day 1, unless archival tissue is available. On-treatment tumor biopsy must be obtained within 7 days of Cycle 2, Day 15 (i.e., between C2D8 and C2D22) and an optional tumor biopsy may be performed for the biomarker cohort or expansion cohorts IVa and Va on C6D15  $\pm$  7 days.

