--	--

	
Q3W for this study.
 
Subjects are required to complete Cycle 1 to be considered evaluable for MTD determination unless discontinuation occurred due to a DLT (i.e., in the dose-determining set).
 
Once the RP2D has been selected, the study will proceed to the Dose Expansion Phase (Phase 2a) to further evaluate RP2D in a larger number of subjects and selected tumor types as described. In the event of unacceptable toxicity in the expansion phase, a lower dose will be explored.
 
Dose Expansion Phase (Phase 2a):
 
The selected arms in Phase 2a, arms I, II, III, IV, and V will follow the Simon's two-stage minimax design in each arm, and 5 arms are planned:
 

○ Arm I : CPI-treated R/R TNBC

○ Arm II : CPI-treated R/R NSCLC

○ Arm III : CPI-treated R/R SCLC

○ Arm IV : CPI-naïve R/R MSS-CRC

○ Arm V : CPI-naïve R/R PC

 
In Stage 1 for arms I, II, III, IV, and V, up to 17 evaluable subjects will be enrolled and treated per arm. If at least one subject achieves objective response (complete response [CR] or partial response [PR]) in an arm, that arm may be expanded by enrolling up to 8 evaluable additional subjects in Stage 2. Study enrollment will continue while the first 17 possible evaluable subjects are undergoing evaluation to confirm response. If no objective response is observed in an arm during Stage 1, further enrollment will be stopped in that arm.
 
Arms IVa (MSS-CRC), Va (PC), and the Biomarker Cohort will not follow the Simon's two-state minimax design. Arms IVa and Va will enroll up to 25 evaluable subjects per arm. NT-I7 will be administered at 1200 ug/kg IM Q6W, with Pembrolizumab fixed dose at 200 mg IV Q3W.
 

○ Arm IVa : CPI-naïve R/R MSS-CRC

○ Arm Va : CPI-naïve R/R PC

 
Biomarker Cohort:
 
The Biomarker Cohort is designed to assess the correlation between tumor infiltrating lymphocytes (TILs) and clinical benefits of NT-I7 in combination with pembrolizumab in subjects with CPI naïve R/R Ovarian Cancer (OC). Up to 10 evaluable subjects will be enrolled to obtain at least 4 pairs of evaluable

--	---

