##### 4.1. Inclusion Criteria

Subjects must meet all the following criteria for study entry:

1. Must be  $\geq 18$  years on the day of signing informed consent.
2. Be willing and able to provide written informed consent/assent for the study.
3. Subjects with histologically or cytologically confirmed advanced or metastatic solid tumors who have disease progression after treatment with all available therapies for metastatic disease that are known to confer clinical benefit, or are intolerant to treatment, or refuse standard treatment.
4. Have measurable disease per RECIST 1.1 as assessed by the enrolling physician. Lesions situated in a previously irradiated area are considered measurable if progression has been demonstrated in such lesions.
5. Subjects enrolling in the Phase 1b and Arms I, IV, IVa, V, and Va of the Phase 2a, and the Biomarker Cohort must have biopsiable disease (i.e., have at least 1 tumor lesion that is accessible and feasible for biopsy) as determined by the enrolling physician. Willing to provide archival tumor tissue sample or newly obtained core or excisional biopsy of a tumor lesion not previously irradiated. Formalin-fixed, paraffin embedded (FFPE) tissue block is preferred to slide. Newly obtained biopsy is preferred to archived tissue.
6. Eastern Cooperative Oncology Group (ECOG) performance status 0-1
7. Subjects must have a life expectancy of greater than or equal to 12 weeks per assessment from the enrolling physician.
8. Subjects must have adequate organ function as defined below:
  - a. Absolute neutrophil count  $\geq 1,500/\mu\text{L}$
  - b. Platelets  $\geq 100,000/\mu\text{L}$
  - c. Hemoglobin  $\geq 9.0 \text{ g/dL}$  or  $\geq 5.6 \text{ mmol/L}$  (Criteria must be met without erythropoietin dependency and without packed red blood cell transfusion within last 2 weeks)
  - d. Total bilirubin  $\leq 1.5 \times$  institutional upper limit of normal (ULN) OR direct bilirubin  $\leq \text{ULN}$  for subjects with total bilirubin levels  $>1.5 \times \text{ULN}$
  - e. AST(SGOT)/ALT(SGPT)  $\leq 2.5 \times \text{ULN}$  (AST and/or ALT  $\leq 5 \times \text{ULN}$  for subjects with liver metastasis)
  - f. Alkaline phosphatase  $\leq 2.5 \times \text{ULN}$  ( $\leq 5 \times \text{ULN}$  for subjects with documented liver involvement or bone metastases)

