Chemistry includes (but is not limited to) sodium, potassium, calcium, phosphorus, chloride, magnesium, bicarbonate, blood urea nitrogen (BUN) or urea, serum creatinine, glucose, uric acid, albumin, total protein, alkaline phosphatase, lactate dehydrogenase, bilirubin (indirect and direct), aspartate serum glutamic oxaloacetic transaminase (AST/SGOT), alanine aminotransferase/serum pyruvic transaminase (ALT/SGPT).

Thyroid function testing: thyroid-stimulating hormone (TSH), free triiodothyronine (T3) (or total T3 for sites where free T3 is not performed), and free thyroxine (also known as free T4)

Serum pregnancy test to be performed at the Screening visit for all females except those surgically sterile or 2 years postmenopausal. Subsequent serum or urine pregnancy tests could be performed as noted or per Investigator's discretion. If the serum screening pregnancy test is performed > 72 hours before first dose, a serum or urine pregnancy test should be repeated prior to dosing.

Urinalysis (a urine dipstick may be used) at Screening and D1 of each cycle.

Baseline CT/MRI tumor imaging must be performed within 28 days prior to first dose for all subjects. Scans performed as part of routine clinical management are acceptable for use as the baseline scan if they are of diagnostic quality and performed within the allotted screening window. The exact same image acquisition and processing parameters should be used throughout the study. The first on-study imaging time point will be performed 6 weeks ( $\pm$  1 week) or earlier if clinically indicated, regardless of any treatment delays, for up to 6 months, and every 9 weeks ( $\pm$  1 week) thereafter. Brain and/or bone lesions may be scanned if applicable. (Note: Subjects do not need to undergo the next scheduled tumor imaging if it is less than 4 weeks after the previous scan.) See Section 13 and [Appendix A – Assessment of Disease](#) for further information.

Biopsy will be performed during screening for those subjects who did not have enough archival tumor tissue and are required to have pre-treatment tumor biopsy per protocol.

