### 12.1. Tumor Tissue for Biomarker Analyses

A key exploratory objective of the study is to make preliminary assessment of biomarkers that may act as pharmacodynamic indicators or predictors of anti-tumor activity of NT-I7 in combination with pembrolizumab. Tumor biopsy sampling is mandatory for all study subjects in Phase 1b and study subjects in specific arms in Phase 2a (i.e., Arm I: CPI-treated R/R TNBC, Arms IV and IVa: CPI-naïve R/R MSS-CRC, Arms V and Va: CPI-naïve R/R PC), and the Biomarker Cohort. In these arms/cohorts, study subjects must have at least one tumor lesion that is accessible and feasible to biopsy and agree to provide paired biopsies in order to participate in this study, unless a written exemption is obtained from the Sponsor.

Tumor biopsy samples will be obtained from each study subject where biopsy sampling is mandatory. The first biopsy will be obtained within 28 days prior to initiation of study drugs in order to establish baseline characteristics of the tumor. Archival samples may be used in place of a fresh biopsy for the baseline treatment sample if the archival tissue was obtained after the last therapy, and is within 28 days of prior to initiation of the study treatment. A second biopsy (on-treatment biopsy) must be obtained within 7 days of Cycle 2, Day 15 (i.e., between C2D8 and C2D22), and before Cycle 3, Day 1 dosing in order to evaluate the effects of the study treatment on the tumor microenvironment. For subjects in CPI naïve R/R OC Biomarker Cohort, the CPI-naïve R/R MSS-CRC expansion IVa cohort and the CPI-naïve R/R PC expansion Va cohort, an optional tumor biopsy may be obtained at Cycle 6, Day 15 ( $\pm$  7 days). For the Biomarker cohort, only in subjects who have dose of NT-I7 increased to 1200  $\mu$ g/kg at C5D1. For subjects who discontinue from study early, every effort should be made to obtain the on-treatment biopsy. For detailed instructions on biopsy sample processing (collection, handling, and shipping), please refer to the *NT-I7 Laboratory Manual*.

Tumor biopsy samples will be evaluated for molecular and histological changes, particularly as these changes pertain to the inflammatory mechanisms. Exploratory biomarker analyses may include, but are not limited to, characterization of PD-L1 expression, quantitation of CD4+ and CD8+ tumor-infiltrating lymphocyte distribution, TCR repertoire analysis, and other molecular assessments.

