1.2 Endpoints

1.2.1 Primary Endpoints

Phase 1b:

- Incidence, nature, and severity of adverse events (AEs) graded according to National Cancer Institute-Common Terminology Criteria for Adverse Events (NCI-CTCAE) v5.0.
- Incidence and nature of dose limiting toxicities (DLTs).
- Potential correlation of dose levels (DLs) with safety and efficacy parameters.

Phase 2a:

- ORR for each individual arm, defined as the percentage of subjects who have at least one confirmed partial response (PR) or complete response (CR), per RECIST 1.1 and iRECIST as determined by the investigator.

Biomarker Cohort:

- Number, distribution, and phenotype of TILs. CD8+TILs in tumor biopsy samples will be identified using a validated immunohistochemistry (IHC) assay and properly certified by a pathologist.

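### Section 5.8 and footnote 17 put no timing or prior-therapy condition on archival baseline tissue, Section 12.1 does, and the SAP's descriptive paired TIL comparison applies neither condition

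*Protocol*

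**What the plan says.** Three places in the current protocol deal with the tissue used as the pre-treatment sample.

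- **Section 5.8, Tumor Biopsy:** fresh tissue "must be obtained within 28 days prior to Cycle 1, Day 1, unless archival tissue is available". The exception is not limited by the age of the archival tissue or by any therapy given since.
- **Section 7.4, footnote 17:** "Biopsy will be performed during screening for those subjects who did not have enough archival tumor tissue". The sentence goes on to limit this to subjects whom the protocol requires to have a pre-treatment biopsy. Its test for archival tissue is quantity.
- **Section 12.1:** archival tissue may stand in for a fresh baseline biopsy "if the archival tissue was obtained after the last therapy, and is within 28 days of prior to initiation of the study treatment".

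Inclusion criterion 5 (Section 4.1) also mentions archival tissue: "Willing to provide archival tumor tissue sample or newly obtained core or excisional biopsy of a tumor lesion not previously irradiated". It is a statement of willingness, and it adds that a new biopsy is preferred.

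The Biomarker Cohort's primary endpoint in SAP 1.2.1 is "Number, distribution, and phenotype of TILs". The protocol synopsis gives the cohort's size: "Up to 10 evaluable subjects will be enrolled to obtain at least 4 pairs of evaluable" (the text available to us breaks off there).

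SAP 2.2 takes as baseline the last value collected before first dose. SAP 4.12 summarises TIL parameters descriptively before and after treatment, by responder status and by PD status, on the safety set. SAP 1.2.3 and Section 6 restrict the pre/on-treatment comparison to samples from the same organ. None of these sections mentions tissue type, collection date or intervening therapy.

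**The concern.** Section 12.1 states what the pair is for: the first sample fixes the tumor's starting state, and the second shows what study treatment did to the microenvironment. That reading fails if another anti-cancer therapy came between the baseline tissue and the first study dose, because the difference then reflects both treatments. The two conditions in Section 12.1 prevent this. Section 5.8 and footnote 17 carry neither condition and do not refer to Section 12.1.

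The subjects are heavily pretreated. The ovarian cohort may have had up to 5 prior lines, so archival tissue could precede one or more of them. Nothing in the SAP would separate such a pair from a clean one in the tables.

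**Working it through.** The plan states no figure on this point, so there is none to reproduce. The check compares the passages and adds simple arithmetic.

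**1. Conditions on archival baseline tissue**

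| Place | Quantity | Age limit | After last therapy | Same organ as on-treatment sample |
|---|---|---|---|---|
| Protocol 5.8 | must be available | none | none | none |
| Protocol 7.4, footnote 17 | enough tissue | none | none | none |
| Protocol 12.1 | none | 28 days | yes | none |
| SAP 2.2, 4.12 | none | none (any time before first dose) | none | none |
| SAP 1.2.3, Section 6 | none | none | none | yes |

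Tissue that satisfies Section 5.8, footnote 17 and the SAP can fail Section 12.1.

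**2. Interval between the two samples**

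Inputs: 21-day cycles (Section 5.1) and the on-treatment window in Section 5.8, "On-treatment tumor biopsy must be obtained within 7 days of Cycle 2, Day 15 (i.e., between C2D8 and C2D22" (visit windows ignored).

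- C2D8 is 21 + 7 = 28 days after C1D1, and C2D22 is 21 + 21 = 42 days after.
- A Section 12.1 baseline lies 1 to 28 days before C1D1.
- Shortest interval: 1 + 28 = 29 days. Longest: 28 + 42 = 70 days. No anti-cancer therapy falls between the baseline tissue and study start.
- Under Section 5.8 and footnote 17 the interval has no upper limit and may span earlier lines.

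**3. Weight of one non-comparable baseline in the Biomarker Cohort**

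Share = k/n, for k such baselines among n pairs.

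- n = 4 (the stated minimum), k = 1: 1/4 = 25%.
- n = 10 (every subject gives a pair), k = 1: 1/10 = 10%.

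**4. What that could do to a mean change**

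Bias in mean change = (k/n) × s, where s is the TIL shift due to the earlier therapy. The documents give no value or direction for s. As an assumption only, take s between 0.5 and 1.0 SD.

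| n | k | Bias, s = 0.5 SD | Bias, s = 1.0 SD |
|---|---|---|---|
| 10 | 1 | 0.05 SD | 0.10 SD |
| 4 | 1 | 0.125 SD | 0.25 SD |
| 4 | 2 | 0.25 SD | 0.50 SD |

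**The case against.** The strongest reply is that the protocol, read as a whole, already contains the right rule. Section 12.1 is the section on tumor tissue for biomarkers, and it alone says when archival tissue may replace a fresh baseline biopsy. Footnote 29 and the arm-specific criteria require pre- and on-treatment biopsies, or willingness to provide them, in the cohorts concerned. Footnote 17 refers back to what the protocol requires. The synopsis schema shows a day −28 to −1 label near its archival-or-biopsy box, which may be the Section 12.1 window, although that figure is broken in the text available to us.

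This is a reasonable reading, but no passage says that Section 12.1 prevails. A site working from Section 5.8 or the schedule would not be directed to it. Even if Section 12.1 governs, the SAP does not exclude or flag tissue that breaches it.

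Other parts of the reply stand and limit the point:

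- A reader might infer that criterion 5 makes archival tissue of any age an accepted baseline. It does not: it concerns willingness to supply tissue, and it prefers new tissue.
- A reader might infer that the Biomarker Cohort's primary endpoint is change in TILs. The endpoint is their number, distribution and phenotype, and the objective is correlation with clinical benefit. The pre/on-treatment comparison of responders with non-responders is labelled exploratory, and SAP 4.12 is descriptive.
- A reader might take 25% as a bias. It is a share of a minimum pair count.

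**Conclusion.** The inconsistency is real and lies in current text. Section 5.8 and footnote 17 accept archival baseline tissue without the timing and prior-therapy conditions of Section 12.1, and the SAP conditions pairs only on organ. The descriptive pre/on-treatment TIL comparison can therefore mix effects of earlier therapy with those of study treatment.

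The consequence is greatest in the Biomarker Cohort, where one such baseline is 10% to 25% of the pairs (10 down to 4). In Phase 1b and Arms I, IV, IVa, V and Va the TIL results are exploratory. The size of any distortion cannot be derived from the documents, and the SD figures above rest wholly on an assumed shift.

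The documents do not support the stronger conclusion that the TIL results are biased. They do not say how many archival baselines fall outside Section 12.1, and there may be none. The finding is that the plan neither prevents such pairs nor makes them visible. No hypothesis test or ORR analysis is affected.

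**What to change.** **Protocol.** Reconcile Section 5.8 and footnote 17 with Section 12.1 for the cohorts where biopsy is mandatory, so that one rule for archival baseline tissue appears in all three places. Leave criterion 5 unchanged: tightening it could narrow eligibility in Arms II and III, where paired biopsy is not mandatory.

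**SAP 4.12, before the paired data are analysed.**

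1. Define the evaluable TIL baseline by the Section 12.1 condition.
2. Summarise paired pre/on-treatment TIL change on pairs that meet it.
3. Show the same summary for all pairs alongside.
4. List tissue type, collection date and intervening therapy for each pair.

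**Cost.** The SAP change uses existing samples and needs no extra biopsy, but it does need the collection date to be on record, which we could not confirm. The main paired summary will have fewer pairs, possibly very few in the Biomarker Cohort, which is why all pairs are also shown. If the protocol passages are aligned to Section 12.1, some future subjects with only older archival tissue could need a screening biopsy. Protocol wording cannot alter baselines in Phase 1b or Arms IV and V, which the protocol describes as completed. For those cohorts only the SAP change helps.
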